2.1.5.3 Two- Dimensional Echocardiography with Complete Doppler Analysis

A complete two-dimensional (2D) echo will be performed utilizing a commercially available GE Vivid-9 or Philips iU33 Echocardiography System. A standard imaging protocol will be performed. The following linear echocardiographic measurements will be obtained (by 2D or M-mode) in both end-diastole and end-systole: left ventricular (LV) internal dimension, septal wall thickness (SWT), and posterior wall thickness (PWT). Quantification of LV mass will be derived by the formula of Devereux RB et al⁸⁴ and by three dimensional-guided modified biplane Simpson’s rule^{85, 86}. LV and left atrial (LA) volumes (systolic and diastolic) will be measured by the biplane method of discs (modified Simpson’s rule). LV ejection fraction and LA function will be calculated from these volume measurements. Doppler measures including peak early (E) and late (A) diastolic velocities from pulsed wave Doppler recordings of the mitral and the tricuspid flow velocities respectively, and E/A ratio will be calculated, along with deceleration time (DT) of early filling velocity and LV isovolumic relaxation time (IVRT). Pulsed-wave tissue Doppler imaging (TDI) will be obtained from the apical 4-chamber view for the lateral mitral annulus, medial mitral annulus and tricuspid annulus. Peak systolic (S), early (e') and late (a') diastolic velocities will be measured. Mitral-to-apical flow propagation will be measured using color M-mode technique.⁸⁷ Color-coded tissue Doppler will be obtained for derivation of global longitudinal strain⁸⁸ and speckle-tissue imaging (STI) on short-axis views to derive radial and circumferential strain and strain rate⁸⁹ according to ASE guidelines.⁹⁰ The myocardial contraction fraction, ratio of stroke volume to myocardial volume, will be calculated as previously described.⁷⁷ Pressure volume based measures including ventricular elastance, arterial elastance, the EDPVR and PVAiso-EDP relations will be estimated as previously described.³⁰

2.1.5.3 Electrocardiogram

A standard 12 lead electrocardiogram will be performed with standard instrument sensitivity of 10 mm = 1 mV. A sum of precordial voltage (sum of S wave in lead V1 plus R wave in lead V₅ or V₆ [SV₁ + RV₅ or V₆]) will be calculated for all electrocardiograms. This sum will be used to compare data from patients with myocardial retention of radiotracer from controls. LVH will be defined when this sum is greater than 35 mm. When the sum was less than 15 mm, low voltage in the precordial leads is present.

Additional criteria to define low voltage only in the limb leads include no QRS deflection greater than 5 mm in any limb lead and low voltage in all leads is present when the average voltage in the three limb leads is <5 mm, and the average voltage in the chest leads is <10 mm.⁹¹ Finally, the mass: voltage ratio will be calculated using the LV mass divided by the sum of S wave in lead VI plus R wave in lead V5 or V6 [SV1 + RV5 or V6]. The ECG tracings will be scanned and uploaded in RedCap.

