1.4.4 Myocardial Contraction Fraction (MCF) to identification and prognosticate in TTR-CA

We previously described the MCF⁷⁴, defined as the ratio of LV stroke volume to myocardial volume and demonstrated that the MCF could successfully distinguish patients with HFpEF from athletes with physiologic hypertrophy and normal controls. The MCF provided a measure of ventricular function independent of chamber size that represents a volumetric measure of abnormal myocardial shortening, which was able to distinguish physiologic from pathologic hypertrophy. Measures of LV chamber performance are based on the premise that the myocardium is nearly incompressible and does not change volume significantly from end-diastole to end-systole.⁷⁵ Capitalizing on this fundamental principle of the incompressibility of the myocardium and by indexing the stroke volume to the myocardial volume, the MCF is an index of the volumetric shortening of the myocardium. During systole, the myocardium shortens and thickens, reducing its contained volume by the stroke volume. The MCF, though operationalized prior to the advent and widespread measurement of strain using echocardiography, is highly correlated with global longitudinal strain.⁷⁶ MCF is analogous to ejection fraction (EF) in that is a ratiometric measure that is easily obtainable, unit less and therefore does not need to be indexed to body size, age or gender. We have shown in a small cohort with cardiac amyloid in whom the average EF was preserved (51.2% \pm 13.1) while the MCF was significantly decreased (29.9% \pm 15.8) and was an independent predictor of survival.⁷⁷ Similar prognostic ability was

confirmed by colleagues at the Mayo Clinic in AL amyloid⁷⁶ and by colleagues in London.⁷⁸ More recently, the prognostic capacity of MCF was confirmed in TTR cardiac amyloidosis in the Transthyretin Amyloidosis Outcomes Survey (THAOS).⁷⁹ Classically, the voltage to mass ratio (V/M) has been employed to identify the phenotype of CA, but its use is confounded by the fact that many elderly patients with amyloid have a paced rhythm, making calculation of the V/M ratio impractical. Preliminary data demonstrates that the MCF with an area under the curve of 0.773 (p<0.0002, 95% CI 0.66–0.86) for identifying TTR-CA was similar to the V/M ratio with an AUC of 0.678 (p=0.07, 95% CI 0.54–0.79). *Accordingly, the MCF has potential as a simple measure to raise suspicion of TTR-CA as well as informing prognosis.*

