Hypothesis 4. Progression of disease: Markers of disease progression are lacking in ATTR CA. We hypothesize that attainment of a hierarchical composite endpoint at 1-year of death, heart failure hospitalization, and 30% decline in 6-minute hall walk will be higher in ATTRm vs. ATTRwt CA. In addition, we will explore the capacity of specific markers to assess disease progression including: (1) established circulating biomarkers such as troponin I/T, NT-proBNP, BNP and Galectin-3, (2) novel biomarkers such as RBP4 and TTR concentration, (3) ECG, and

echocardiographic measures including longitudinal strain and MCF, (4) functional capacity by 6-minute hall walk and SPPB, and (5) QOL. Our preliminary data and published work⁹ suggests reduced median survival for ATTRm Val122Ile CA (25 months) vs ATTRwt (43 months) in different race cohorts. We hypothesize that we will observe reduced survival and greater functional decline in ATTR Val122Ile vs ATTRwt within race cohorts.

Hypothesis 5. Performance of risk calculator: Our point-of-care risk calculation utilizing RBP4 and TTR concentration with echocardiographic and ECG determined parameters will be tested in this cohort. We will re-derive the prediction model based upon clinical variables noted above. We anticipate showing a similar degree of accuracy (ROC AUC > 0.95) for identification of cases with ATTR vs. controls

Specific Aim 2: To demonstrate that circulating RBP4 concentration is integral to TTR tetramer stability, which in turn determines the clinical characteristics of ATTR CA. We will measure TTR tetramer stability and RBP4 concentration in serum and urine collected in Aim 1. The overall hypotheses of this Aim are that measurements of TTR kinetic stability, RBP4 and TTR concentration will differentiate patients with ATTR CA vs. non-amyloid HF controls and associate with disease progression and outcomes. Specific hypotheses are as follows:

Hypothesis 1: TTR kinetic stability and RBP4 concentration: We hypothesize that at baseline, TTR kinetic stability will be lower in ATTR CA vs. non-amyloid HFpEF, and that stability will be inversely proportional to plasma RBP4 concentration. We further hypothesize that TTR kinetic stability will be lower for ATTRm vs. ATTRwt.

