2.1.8 Data Analysis Plan

Descriptive statistics will be used to summarize subjects' demographics and study outcomes. Sample proportions with exact 95% confidence intervals will be used to estimate the overall prevalence of ATTRm CA in Blacks and Hispanics and by sex. All analyses will be performed in SAS v.9.4 (Cary,NC), at a significance level of 0.05.

AIM 1: Hypotheses 1-3: The differences in proportions for prevalence (#1), genetic mutation status (#2), and sex (#3) will be assessed using Chi-squared/Fisher Exact tests. The genetic ancestry analysis will use 500K SNP data to perform principal components analysis (PCA) and determine the percentage of African admixture in all participants. To identify the associations of rare genetic variants in the TTR gene in ATTR CA cases vs controls, we will utilize burden testing.⁹⁴ **Hypothesis 4:** The main analysis will use the Kaplan-Meier method to estimate the probabilities of the composite endpoint, with medians (95% CI) being reported for each group. Cox regression analysis will be performed to generate the hazard ratio (95% CI), and to allow adjustment for other covariates such as sex or race/ethnicity, or explore interaction with other variables including cardiac biomarkers, echo parameters, or QOL. Alternatively, we will apply and compare Finkelstein-Schoenfeld's unmatched approach⁹⁵ to the matched win ratio,⁹⁶ both methods being used for reporting composite endpoints, with more appropriate priority given to the more clinically important event, e.g. mortality. **Hypothesis 5:** We will test the clinic-based risk calculator that was previously developed and validated in a smaller matched cohort study.⁹⁷ The proposed 4-variable model included: RBP4, LVEF, inter-ventricular septal thickness, mean limb lead QRS voltage, and generated an ROC AUC >90%. This model will be tested in our larger cohort and assessed with respect to prediction capability (AUC ROC) and goodness-of fit (Hosmer-Lemeshow test). We also plan to fit additional multivariable logistic regressions using the variables collected employing variable selection/model-building strategies and comparing the

resulting model(s) to the one proposed above. The variables in the final clinical risk model will be based on weights from the multivariate model.

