Ventricular Rate(bpm) _____

Total QRS Voltage (mm) _____

PR Interval (msec) _____

Low QRS Voltage Yes No

QRS Axis (degrees) _____

QT Interval (msec) _____

QRS Duration (msec) _____

QTc Interval (msec) _____

SV₁ + RV₅ or V₆ (mm) _____

Overall Assessment

Rhythm

Sinus Rhythm Atrial Fibrillation

Ventricular Conduction Defect Yes No

Other, specify: _____

If yes, Left Bundle Branch Block

Electrical Pacing on ECG Yes No

Incomplete Left Bundle Branch Block

If yes, Atrial Pacing

Left Anterior Hemiblock

Ventricular Pacing

Left Posterior Hemiblock

Atrial Ventricular Pacing

Right Bundle Branch Block

ST or T-wave changes Yes No

Incomplete Right Bundle Branch Block

If yes, specify reason:

Intraventricular Conduction Delay

A-V Block Yes No

Infarct pattern/Poor R-wave progression Yes No

If yes, 1st degree

If yes, infarct pattern is observed in this locations:

2nd degree, Type I

Anteroseptal

2nd degree, Type II

Anterior

3rd degree heart block

Anterolateral

Other, specify: _____

Lateral

Inferior

Other, specify: _____

Form Completed by: _____ Investigator's Signature: _____

SHORT PHYSICAL PERFORMANCE BATTERY (SPPB)**1. Balance Tests****a. Side-by-Side Stand**

Held for 10 s → 1 point
 Not held for 10 s Time: ____ . ____ s → 0 points, go to #2
 Not attempted

b. Semi-Tandem Stand

Held for 10 s → 1 point
 Not held for 10 s Time: ____ . ____ s → 0 points, go to #2
 Not attempted

c. Tandem Stand

Held for 10 s → 2 point
 Held for 3 to 9.99 s → 1 point
 Held for < than 3 s → 0 points
 Not attempted

d. Balance Ordinal Score: ____ (sum points)

If not attempted, select reason:

1 Tried but unable
2 Participant could not hold position unassisted
3 Not attempted, you felt unsafe
4 Not attempted, participant felt unsafe
5 Participant unable to understand instructions
6 Other (specify): _____
7 Participant refused

2. Gait Speed Test**a. Test #1**

Time for 4-meter: ____ . ____ s

b. Test #2

Time for 4-meter: ____ . ____ s

c. Walking aid None Cane Walker**d. Record best of the two times**

Best time: ____ . ____ s

If not attempted, select reason:

1 Tried but unable
2 Participant could not walk unassisted
3 Not attempted, you felt unsafe
4 Not attempted, participant felt unsafe
5 Participant unable to understand instructions
6 Other (specify): _____
7 Participant refused

e. Gait ordinal score: ____

Could not do

>8.70 s

6.21-8.70 s

4.82-6.20 s

<4.82 s

3. Repeated Chair Stand Test**a. Safe to stand five times?**

Yes No

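### ECG voltage measures are planned on every tracing with no rule for ventricular pacing, although the protocol itself says paced rhythm confounds the voltage-to-mass ratio

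*Combined protocol and SAP*

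**What the plan says.** **Voltage measures.** Section 2.1.5.3 (Electrocardiogram) says the sum SV1 + RV5/V6 "will be calculated for all electrocardiograms. This sum will be used to compare data from patients with myocardial retention of radiotracer from controls". It defines LVH as a sum above 35 mm and low precordial voltage as a sum below 15 mm. It then adds: "Finally, the mass: voltage ratio will be calculated using the LV mass divided by the sum of S wave". No exception is made for paced rhythm.

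**Risk calculator.** Section 2.1.8, Hypothesis 5, lists the four variables as "RBP4, LVEF, inter-ventricular septal thickness, mean limb lead QRS voltage". The model is to be assessed by ROC AUC and the Hosmer-Lemeshow test. Section 2.1.6 says the calculator will also be re-derived, and anticipates an AUC above 0.95.

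**Pacing.** Section 1.4.4 says of the voltage-to-mass ratio that "its use is confounded by the fact that many elderly patients with amyloid have a paced rhythm, making calculation of the V/M ratio impractical", and puts forward the myocardial contraction fraction (MCF) as a simple alternative. The exclusion criteria do not mention pacemakers. In Appendix 4, the baseline history asks about pacemakers, and the ECG form has an item "Electrical Pacing on ECG" with atrial, ventricular and atrial-ventricular as types.

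Nowhere do the documents exclude paced tracings, set their voltage to missing, adjust for pacing or plan a sensitivity analysis.

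**The concern.** The background section gives a reason not to trust a voltage-based measure in paced patients, and the methods section then computes that kind of measure on every tracing. With ventricular pacing, the QRS amplitude reflects the paced activation sequence. Entered as native voltage, it is a mismeasured predictor.

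Two analyses are exposed. One is the ECG comparison of tracer-positive patients with controls, including the two flags and mass:voltage. The other is Hypothesis 5, where limb-lead voltage is one of four predictors and the model may also be refitted. If paced amplitude carries little information about amyloid, the voltage signal is diluted and a refitted model may give voltage too little weight. If the rule is left until the data are in hand, the reported AUC depends partly on an analyst's later choice.

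**Working it through.** The plan states no figure on this point, so there is none to reproduce. The check is of the text, followed by a rough size.

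**1. Is there a conflict?** Section 1.4.4 calls the voltage-to-mass ratio confounded and impractical in paced patients. Section 2.1.5.3 computes mass:voltage, and the sum it rests on, without exception. Paced patients can enrol, and pacing type is recorded but not used. The gap is in the analysis rule, not in data capture.

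**2. How many cases might be paced?** Table 1 (section 1.2.3) gives a pacemaker in 11.00% of 57 ATTRwt and 1.20% of 31 V122I patients. Both groups are small, and the second figure cannot be a whole-patient count: 0.012 × 31 = 0.37, whereas one patient would be 3.2%.

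Weighting by the planned case mix:
- ATTRm (section 2.1.7): 0.08 × 600 + 0.04 × 200 = 48 + 8 = 56.
- ATTRwt: 2-8% of 800 = 16-64. This is an assumption, because section 2.1.6 gives that range for Hispanics only.
- Low end: (56 × 0.012 + 16 × 0.11) / 72 = 2.43 / 72 = 3.4%.
- High end: (56 × 0.012 + 64 × 0.11) / 120 = 7.71 / 120 = 6.4%.

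That is about 3-10 of the expected 80-160 cases (0.034 × 80 = 2.7; 0.064 × 160 = 10.2). The share in controls is not given. I assume 3-6% in each group.

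**3. What does that do to a voltage-only AUC?** Assume normal voltages with SD 1, cases lower than controls by d = √2 · Φ⁻¹(A), where A is the AUC with no pacing. Paced values have mean m above the control mean and carry no disease information. With p of cases and q of controls paced:

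AUC = (1−p)(1−q)A + (1−p)q·Φ((d+m)/√2) + p(1−q)·Φ(−m/√2) + 0.5pq

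With m = 0 this reduces to (1−p)A + 0.5p, whatever q is. For A = 0.80 and p = 0.06: 0.94 × 0.80 + 0.03 = 0.782.

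With m = 1, A = 0.80 and p = q = 0.06: 0.7069 + 0.0530 + 0.0135 + 0.0018 = 0.775.

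| Cases / controls paced | A = 0.80, m = 0 | A = 0.80, m = 1 | A = 0.90, m = 0 | A = 0.90, m = 1 |
|---|---|---|---|---|
| 3% / 3% | 0.791 | 0.787 | 0.888 | 0.883 |
| 3% / 6% | 0.791 | 0.792 | 0.888 | 0.885 |
| 6% / 3% | 0.782 | 0.771 | 0.876 | 0.863 |
| 6% / 6% | 0.782 | 0.775 | 0.876 | 0.866 |
| 11% / 5% | 0.767 | 0.746 | 0.856 | 0.832 |
| 1.2% / 1.2% | 0.796 | 0.795 | 0.895 | 0.893 |

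So 0.80 becomes about 0.77-0.79 and 0.90 about 0.86-0.89 at 3-6% paced. The last two rows show what follows from applying one genotype's Table 1 share to all cases. The 5% for controls in the 11% row is an assumption.

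**4. What cannot be computed.** The documents give neither the joint distribution of the four predictors nor the weight on voltage, so the effect on the calculator is unknown.

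**The case against.** Several points on the other side stand.

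- Section 1.4.4 speaks of the voltage-to-mass ratio, not limb-lead voltage. Carrying the concern over to the calculator is an inference; it is reasonable because both use QRS amplitude.
- Atrial-only pacing with native conduction leaves the QRS unchanged, so a claim about all paced participants would be too wide.
- The calculator is described as a point-of-care tool to be tested in this cohort, which admits paced patients. For that population the all-participant AUC is a legitimate measure of accuracy. A reader might infer that the unpaced result should be the main one; the documents do not support that, because it would change the target population.
- The synopsis lists the calculator among exploratory items. Pacing type is recorded, tracings are uploaded, MCF is already measured and further models are planned. Nothing is lost irrecoverably.

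A reader might also take the 11% in Table 1 as the paced share of all cases. It is the ATTRwt figure only, and the same row gives 1.2% for V122I, the genotype the protocol expects to predominate in Black participants (600 of 800). Nor is it supported that pacing would reverse the low-voltage signal: every scenario above shows attenuation or almost no change.

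None of this supplies the missing rule. An instruction covering all tracings still stands beside a statement that the derived ratio is impractical in paced patients.

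**Conclusion.** The point holds at minor severity. Followed as written, the plan analyses paced QRS amplitude as native voltage on tracings with ventricular or atrial-ventricular pacing. That probably attenuates the case-control voltage comparison, the LVH and low-voltage flags and mass:voltage, and by extension the voltage term in the calculator.

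The effect is probably modest: a loss of about 0.01 to 0.03 from a voltage-only AUC of 0.80. This rests on 3-6% of cases and controls being paced, on paced amplitude carrying no disease information, and on pacemaker share standing in for ventricular pacing on the tracing. None of these is established by the documents. A reader might infer that the calculator's accuracy falls by a similar amount; that cannot be derived from them. Prevalence is unaffected, because cases are defined by scintigraphy.

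**What to change.** **Section 2.1.5.3 (Electrocardiogram).** Limit the voltage sum to *all electrocardiograms without ventricular or atrial-ventricular pacing*, using the pacing item on the ECG form. On other tracings, code the sum, the LVH and low-voltage flags and mass:voltage as not evaluable. Atrial-only pacing stays in.

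**Section 2.1.8, Hypothesis 5.** Report the calculator's AUC and calibration both in all participants and with ventricular-paced tracings excluded. When the model is re-derived, exclude or flag paced voltages. State this before the data are analysed. A separate MCF-based model for paced patients should not be required: with about 3-10 paced cases it could not be evaluated.

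**Cost.** Analysis wording and a filter, with no new data. A small share of records drops out of the voltage analyses, and the voltage comparison then applies only to tracings without ventricular pacing.

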2.1.5.4 Laboratory Analysis

Blood will be drawn and analyzed for standard chemistry (Chem-7), liver function, BNP, NT-proBNP, galectin-3, troponin I and T, vitamin A, retinol binding protein 4 (RBP4) and prealbumin. BNP, TnT, Gla-3, TnI and NT-proBNP will be measured through a research agreement with Abbott Laboratories, while the others are measured by local or affiliated research laboratories. Additionally, the kinetic stability of plasma TTR will be assessed at Scripps Laboratories using the published subunit exchange strategy, in which recombinant tagged TTR homotetramers are added to human TTR in plasma at equal concentrations to measure the rate at which the subunits exchange⁸⁰. Tetramer dissociation is the rate-limiting step for subunit exchange and for amyloidogenesis. We hypothesize that those individuals at risk for developing WT ATTR-CA produce WT TTR exhibiting inferior kinetic stability. Quantification of TTR kinetic stabilization could serve as a surrogate biomarker for the prediction of clinical outcomes and could become part of a risk calculation or an early diagnosis strategy, after validation. Additional aliquots will be used for genetic analysis (see below) and stored at -80° for analysis in the future. Ancestry analysis will also be performed on all participants. Urine specimen will be analyzed for Vitamin A and RBP4 measurements, to learn whether its levels differ among subjects with TTR amyloidosis, and to learn more about the specific physiology of the disorder.

TTR Gene Sequencing: Genotyping will be performed on genomic DNA obtained from blood from participants for the Val122Ile mutation using a PCR-based assay in the CLIA certified laboratory at Boston University.

Ancestry Analysis: Ancestry information will be obtained after buffy coat samples are extracted from participants' blood. Analysis for ancestry will take place in a specialized laboratory at Columbia University.

CCRLE and NIH Repository: Several specimens collected during the study will be stored indefinitely in a -80°C freezer located at the CCRLE lab and used for future analysis. Some of these samples will ultimately be transferred to a NIH repository.

2.1.5.5 QOL Questionnaires

Two quality of life scales will be employed including two disease specific measures: the Kansas City Cardiomyopathy Questionnaire (KCCQ) and a more general instrument, the 12-Item Short Form Survey (SF-12v2).

2.1.5.6 Health Literacy Questionnaire

The participants' capacity to handle health -related information will be assessed with four instruments: Health Literacy, Trust, Perceived Discrimination, and English Proficiency.

2.1.5.7 Functional Capacity

Functional capacity will be determined by a hall walk of six minute duration⁹² and a short physical performance battery.⁹³

